8.9 ICG Injections

ICG (25 mg vial) will be reconstituted with 10 ml sterile water provided by the manufacturer; further dilutions will be made in saline to achieve the final concentration of 0.32 ml, or 250 µg/ml ICG. Up to 16 intradermal injections, each consisting of 0.1 mL or less, using conventional 30 or 31-gauge needles may be administered by a clinician. However, typically each subject will only receive 8 intradermal injections in the arms and the additional 8 injections may be administered if the clinician identifies areas of lymphatic drainage that may not be covered by the typical injections. Subjects will typically receive 2 injections in the

dorsum of each hand and 2 in each medial wrist. Subjects will not receive more than 400 µg of ICG.

Vital signs (blood pressure, heart rate, temperature) and redness or inflammation at the injection sites will be monitored and recorded at baseline (pre-injection of ICG) and at 15 and 30 minutes after the initial injection. Study subjects will be contacted between 18 and 28 hours after ICG administration to ensure no adverse events have occurred

8.10 MoistureMeterD Measurements

Local tissue water (LTW) measures will be obtained using the FDA-cleared MoistureMeterD™ (MMD) with the M25 (2.5 mm) and L50 (5.0 mm) probes (Delfin Technologies, Finland). This non-invasive, rechargeable, battery-operated device and technology has been demonstrated to provide a measure of LTW and its change based on measurements of the skin's tissue dielectric constant at a frequency of 300 MHz. The method has been widely used in clinical studies as a highly sensitive measurement of water content and edema in the skin and subcutis (16-19). There are no risks associated with the use of this data collection device. In addition, data collected from this device will not be used in the diagnosis or treatment of lymphedema.

The MMD measurements will be performed on the affected and unaffected side before and after treatment. Measurements may only be conducted by research personnel with documented training showing the individual was able to independently and accurately conduct the measurements.

The following measurement procedures will be followed to assess the upper extremity tissue dielectric constant (TDC) values as indices of skin/tissue water:

- Ensure the subject remains in a seated position with the arms relaxed
- Turn on the MoistureMeter D unit, select the correct probe size on the display, and wait for the word “wait” to disappear from the display before taking any measurements.
- Measure and record the TDC values at sites A, B, and C (See Figures 3-5) by firmly placing the probe on the marked site such that the entire probe depresses the skin and leaves a slight indentation.
- All measurements will be made in duplicate using the L50 (5 mm) probe alternating in a consistent fashion (A, B, C, A, B, C) to ensure tissue water is not displaced at the time the second measurement is taken.
- Clean the L50 probe with an antiseptic cleansing towel or ethanol and return to the storage case.
- Repeat steps 1 through 5 (in duplicate) using the M25 (2.5 mm) probe.
- Turn off the MoistureMeterD unit, clean the M25 probe with an antiseptic cleansing towel or ethanol, and return both the probe and MoistureMeterD unit to the storage case.

8.11 Ultrasound

Tissue ultrasound measurements will be collected from the affected and unaffected arms using a 4-13 MHz linear transducer with the probe placed longitudinally on

the tissue. Measurements may only be conducted by a study team member with documented training. Field size and gain may be adjusted as necessary to optimize image quality and boundary definition.

Ultrasound measurements will be taken to assess the thickness of the epidermis (skin) and the thickness of the subcutaneous layer from the epidermis (skin) to the muscular fascia. When the dermo-hypodermal junction is clearly identified, the full skin thickness (epidermis and dermis) from the anterior echogenic border of the epidermis to the posterior echogenic border of the dermis may be measured in B-mode. Subcutaneous tissue thickness is measured as the distance between the posterior echogenic border of the dermis and the anterior echogenic border of the muscular fascia. When the dermo-hypodermal junction or the muscular fascia is not clearly identified, measurements will not be performed, and the reported result will be classified as a “blurred border.”

The following measurement procedures will be followed to assess skin thickness:

- Ensure the subject remains in a seated position with the arms relaxed
- Measure and record skin and subcutaneous thickness measurements at sites A, B, and C (See Figures 3-5)

Additional guidance on ultrasound measurements and analysis will be provided in an ultrasound user guide.

8.12 NIRF Imaging

After all injections are made and the water content and skin thickness measurements are made, NIRF imaging will commence. From the images of each region, the lymphatic activation (anatomy and propulsion) will be quantified as follows:

- Intact, fluorescent lymphatic vessels observed before and after the treatment will be recorded as an increase in vessels, decrease in vessels, or no change. The two-dimensional, projected area or extent of dermal backflow, before and after treatment, will be quantified using ImageJ (NIH, Bethesda, MD) by adjusting the brightness of the images to 20% of the maximum pixel value and measuring the area of regions of interest drawn around fluorescent areas not associated with intact and well-defined (i.e., “normal”) lymphatic vessels.
- The rate of lymphatic propulsion events observed immediately before and after treatment will be quantified by counting the total number of propulsion events observed and dividing by the total observation time at each region of interest.

Prior to injection and after NIRF imaging is complete, digital photographs of the arms will be acquired. Images of the front and back of the arms will be acquired with the subject standing up and the arms held out away from the sides.

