5.1 Endpoints

To compare the effects of FT to FT-SW in BCRL patients after one treatment based upon:

- Lymphatic activation in the affected and contralateral limb using the investigational technique of near infrared-fluorescent (NIRF) imaging
- Swelling in the affected and contralateral limb as assessed using:
 - Perometry (LymphaTech 3D Scanner)
 - Local tissue water content (MoistureMeterD)
- Skin changes on the affected and contralateral limb as assessed by:
 - Skin thickness (Ultrasound)
- Safety

Table 1. Outcome Measures

Endpoint	Outcome Measure
Lymphatic activation	
 Proportion of subjects who show an increase in the number of functional vessels and/or area of dermal backflow per NIRF imaging of the affected and contralateral arm when comparing post-treatment values to pre-treatment values Proportion of subjects who show an increase of lymphatic propulsion events immediately after treatment
Changes in Swelling	
 Proportion of subjects who show a decrease in arm perometry (limb volume) when comparing post-treatment values to pre-treatment values for the affected and contralateral arm Proportion of subjects who show a decrease in local tissue water at target sites when comparing post-treatment values to pre-treatment values for the affected side Mean change in perometry and local tissue water post-treatment will be compared for all sites
Skin Changes	
 Proportion of subjects who show a decrease in skin thickness at target site when comparing post-treatment values to pre-treatment values for the affected side Mean change in skin thickness post-treatment will be compared for all sites
Safety	
 Adverse events will be presented in data listings

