6.2 Randomization

Randomization will occur after all of the screening/baseline assessments are complete. The study personnel performing study assessments will remain blinded to the treatment assignment.

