8.14 Treatment

After all pre-treatment assessments have been performed, the subject will undergo the treatment that they have been randomized to. The personnel administering the treatment will not perform any study assessments as they will be unblinded to the treatment. If the subject has been randomized to the FT-SW, treatment will begin approximately 20 minutes after they enter the room where treatment is being performed to ensure the blinded study staff remain unaware of the treatment allocation.

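### The NIRF vessel outcome is a direct before/after judgement, and the plan masks assessors to treatment arm but nowhere masks the NIRF reader to time point

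*Combined protocol and SAP*

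**What the plan says.** **Masking.** Section 6.2 states: "The study personnel performing study assessments will remain blinded to the treatment assignment". Section 6.3 keeps the staff who give treatment away from assessments. Section 8.14 delays the start of FT-SW by about 20 minutes "to ensure the blinded study staff remain unaware of the treatment allocation". All three measures concern treatment arm. No section addresses masking to time point, the order in which images are read, the number of readers, or a check of agreement between reads. Section 6.0 says that the investigator collects and records the NIRF data.

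**Measurement (Section 8.12).** Three NIRF items are defined, and they differ in kind:
- Vessels: "Intact, fluorescent lymphatic vessels observed before and after the treatment will be recorded as an increase in vessels, decrease in vessels, or no change". What is recorded is the change itself, not two counts.
- Dermal backflow: an area for each time point, at a brightness setting of 20% of the maximum pixel value, obtained by "measuring the area of regions of interest drawn around fluorescent areas not associated with intact and well-defined" vessels.
- Propulsion: a rate for each time point, from "counting the total number of propulsion events observed and dividing by the total observation time at each region of interest".

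**Outcome (Section 5.1, Table 1).** The first NIRF outcome is "Proportion of subjects who show an increase in the number of functional vessels and/or area of dermal backflow per NIRF imaging". The second is "Proportion of subjects who show an increase of lymphatic propulsion events immediately after treatment". NIRF is listed first, but no endpoint is named as primary.

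**Objective and analysis.** Section 4.0 aims to show equivalency on objective measurements. Section 16.0 plans percentages with 95% confidence intervals, gives no margin, and plans no formal test.

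**The concern.** Masking to arm stops a reader from favouring one device. It does nothing about a belief that compression works whichever device was used. The protocol states such a belief: Section 11.1.1 expects treatment to make the lymphatics contract more often. A reader who knows which image came second, and who must choose between an increase, a decrease and no change, may resolve doubtful pairs as an increase.

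An error of that kind is common to both arms, but it is not harmless here. Each arm's proportion is reported in its own right, with an interval that does not allow for reader error. When the stated aim is to show that two devices are alike, an error that draws the two proportions together favours that aim. Enrolling more subjects would not remove it. Section 17.0 intends the data for product development and marketing claims, so the descriptive proportions may carry weight even though nothing is tested.

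**Working it through.** **1. What can be reproduced.** The plan gives 20 subjects, at least 10 per arm, with no expected rates, margin, alpha or power. There is no figure of the plan's own to reproduce. The true rates and miscall rates below are assumptions. Only the 10 per arm is the plan's.

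**2. Is one call enough?** Table 1 joins vessels and backflow with and/or. A vessel increase therefore makes a responder whatever the backflow area does.

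**3. Model for the vessel item.** Let p be the true proportion with an increase, and q the share of true non-increases called an increase, the same in both arms because the reader is masked to arm.
- Observed proportion: p' = p + (1 - p)q
- Observed difference: p1' - p2' = (p1 - p2)(1 - q)

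**4. Illustration, assumed true rates 40% and 70% (difference 30 points).**

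| q | Lower arm | Higher arm | Difference |
|---|---|---|---|
| 0 | 40% | 70% | 30 points |
| 0.25 | 0.40 + 0.60 x 0.25 = 55% | 0.70 + 0.30 x 0.25 = 77.5% | 22.5 points |
| 0.5 | 0.40 + 0.60 x 0.5 = 70% | 0.70 + 0.30 x 0.5 = 85% | 15 points |

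The shrinkage is 7.5 to 15 points. If p1 = p2 it is zero, although both proportions are still inflated.

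**5. Sampling error on the same rates.** With 10 per arm, the approximate 95% half-width of the difference is 1.96 x sqrt(0.40 x 0.60/10 + 0.70 x 0.30/10) = 1.96 x sqrt(0.045), about 42 points. That is well above the shrinkage.

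**6. Chance that the arms look alike.** For assumed true rates of 80% and 50%, exact binomial enumeration at 10 per arm gives the chance that the observed proportions differ by 20 points or less. The 20-point band is also an assumption.

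| q | Expected difference | Chance of 20 points or less |
|---|---|---|
| 0 | 30 points | 39% |
| 0.1 | 27 points | 45% |
| 0.2 | 24 points | 51% |
| 0.3 | 21 points | 58% |
| 0.5 | 15 points | 73% |

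Starting from 60% v 30%, 50% v 20% or 90% v 60%, the chance is again 39% at q = 0 and reaches 66% to 77% at q = 0.5.

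**7. Other forms of error.**
- *Equal points added to both arms.* The difference does not shrink. But adding 15 points to 40% and to 70% means miscalling 15/60 = 25% of non-increases in one arm and 15/30 = 50% in the other. A common miscall rate is the more natural model for a reader masked to arm.
- *Miscalls both ways.* If a share r of true increases is also missed, p' = p(1 - r) + (1 - p)q = q + p(1 - q - r), and the difference is multiplied by (1 - q - r). It shrinks further while q + r < 1. The level of each proportion may then move up or down.

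**The case against.** The strongest reply has five parts.

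*The documents do not show unmasked reading.* A reader might infer that the NIRF reader knows the time point and that the call is therefore biased upward in both arms. The text does not support either statement as fact. It does not say who reads the images, when, or in what order. What stands is narrower: masking to time point is not provided for, and the vessel item as written is a before/after comparison.

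*An upward direction is not established for the whole composite.* Section 3.2.3 treats dermal backflow as an abnormal signal. A reader hoping for improvement might draw the later regions smaller, which would lower that component. This stands. The upward risk belongs to the vessel call.

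*The three items are not equally subjective.* Backflow already has a measured area per time point, and propulsion a count over time. This stands too, although both still depend on the reader.

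*There is no equivalence decision to distort.* A reader might infer that the trial is pushed towards passing an equivalence test. Section 16.0 sets no margin and plans no test, so only estimates and an informal conclusion can be affected. Imprecision at 10 per arm is the larger problem. That limits the point without removing it, because the planned intervals show sampling error and not reader error.

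*Masked reading may be only partly achievable.* ICG injection is scheduled only at screening/baseline, and post-treatment imaging follows roughly an hour or more after the baseline images (60 minutes of treatment, or a wait of about 20 minutes plus 40). Dye distribution may often give the time point away. This is a real limit on the remedy. It is not a reason to keep a recorded judgement of change where a count per image could be used.

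**Conclusion.** The concern holds in a limited form. The plan protects against a reader favouring one arm, but has no protection against an expectation of activation shared by both. The exposed item is the vessel call, which can by itself decide responder status. Dermal backflow is less exposed, with the direction of any bias uncertain, and propulsion is less exposed as well.

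The possible consequences are inflated proportions with a vessel increase in each arm and, if the arms truly differ, a difference reduced by the factor (1 - q). A 30-point difference would become 22.5 points at q = 0.25 and 15 points at q = 0.5. This rests on a common, one-way miscall rate and on assumed rates. The documents give no basis for the size of q, and there is no shrinkage if the arms do not differ. The effect is smaller than the sampling error at 10 per arm, and it bears on description rather than on a formal test. The change is cheap and worth making before images are read.

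**What to change.** In Section 8.12, replace the vessel comparison with a count per image, read as follows:
- Stored images have their time labels removed and are presented in random order.
- The same arm-masked reader records a vessel count for each image on its own, in place of the three-way change call.
- Backflow regions are drawn and propulsion events counted under the same masking.
- The analyst derives change by program from the recorded values.

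**Cost.** File renaming and a random order list. The reader, the images and the subjects' procedures stay the same.

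**Limits.** Dye distribution may often reveal the time point. Masking is weaker if the reader also acquired the images, so the section should say whether that is the case. Masked reading cannot remove a true change in the images with time since ICG injection. With no untreated arm, the single-arm proportions should not be read as pure treatment effects even after this change.

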4.0 Study Objective

The objective of the study is to demonstrate equivalency in treatment effect, as determined by objective measurements, between the novel simultaneous therapy cycle software and the FDA-cleared FT.

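### Vessel change is recorded only as a direction (increase, decrease, no change), so the planned vessel summary cannot show the size of the gain and can saturate

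*Combined protocol and SAP*

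**What the plan says.** All references are to the combined protocol and SAP.

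- **Section 8.12 (NIRF Imaging), opening:** "From the images of each region, the lymphatic activation (anatomy and propulsion) will be quantified as follows".
- **Section 8.12, vessels:** "Intact, fluorescent lymphatic vessels observed before and after the treatment will be recorded as an increase in vessels, decrease in vessels, or no change".
- **Section 8.12, the other two NIRF items:** dermal backflow is measured as an area in ImageJ before and after treatment. The propulsion rate "will be quantified by counting the total number of propulsion events observed and dividing by the total observation time at each region of interest".
- **Section 5.1, Table 1, lymphatic activation:** "Proportion of subjects who show an increase in the number of functional vessels and/or area of dermal backflow per NIRF imaging", comparing post-treatment with pre-treatment values for the affected and contralateral arm. No mean change is listed for any NIRF measure.
- **Section 5.1, Table 1, other endpoints:** "Mean change in perometry and local tissue water post-treatment will be compared for all sites", and "Mean change in skin thickness post-treatment will be compared for all sites".
- **Section 4.0:** the aim is to "demonstrate equivalency in treatment effect, as determined by objective measurements".
- **Section 16.0:** percentages with 95% confidence intervals for categorical data, a focus on estimation, and no formal hypothesis tests. No equivalence margin is given.

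**The concern.** Table 1 defines the outcome by a number of vessels, but the recording rule in Section 8.12 does not ask for that number. Within any one reading, a gain of one vessel and a gain of five give the same entry. For perometry, local tissue water and skin thickness, Table 1 plans a mean change as well as a proportion, so the sponsor treats size of change as relevant. For vessels, a mean change cannot be computed from what is recorded.

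The direction of the loss matters because the aim is equivalency. Once most subjects in both arms gain at least one vessel, the proportion with an increase sits near 100% in each arm and stops responding to the size of the gain. The session lasts about 40 minutes with FT-SW and about 60 with FT (Section 5.4), so a smaller effect on FT-SW is the question of interest. On this measure a smaller effect could go unseen, and the error would favour apparent similarity.

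**Working it through.** The plan has no vessel-count figure, SD, margin or power statement, so there is nothing of its own to reproduce. The only planning input is 20 subjects, at least 10 per arm, 1:1 (Synopsis; Section 5.3). All vessel gains and SDs below are assumptions.

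**1. A case that needs no distribution.** Every FT subject gains 4 vessels and every FT-SW subject gains 2.
- With the direction call, each arm reads 10/10. The Clopper-Pearson lower limit is 0.025^(1/10) = 0.69, so each arm is reported as 100% (69% to 100%).
- The difference is 0. The Wilson lower limit for 10/10 is 10/(10 + 1.96²) = 0.722, so Newcombe's 95% interval is ±(1 − 0.722), or about ±28 points.
- With counts, the difference FT-SW minus FT is 2 − 4 = −2 vessels.

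**2. How the proportion saturates.** Take the change in count as a normal draw with mean μ and SD σ, rounded to a whole number. Then P(increase) = 1 − Φ((0.5 − μ)/σ). For σ = 1.5:
- μ = 4: (0.5 − 4)/1.5 = −2.33, giving 99%.
- μ = 2: (0.5 − 2)/1.5 = −1.00, giving 84%.

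At σ = 1 the pair is 100% v 93%; at σ = 2 it is 96% v 77%.

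**3. How often a 95% interval for the arm difference excludes zero, 10 per arm.** Counts: Welch interval, 20,000 simulated trials per cell (simulation error under 1 point). Proportion: Newcombe interval, summed exactly over the two binomial distributions. If FT reads 10/10, that interval excludes zero only when FT-SW reads 6/10 or fewer.

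| FT v FT-SW mean gain | Summary | SD 1 | SD 1.5 | SD 2 |
|---|---|---|---|---|
| +4 v +2 | counts | 98% | 79% | 55% |
| | proportion | 0.3% | 5% | 12% |
| +3 v +1.5 | counts | 85% | 55% | 35% |
| | proportion | 6% | 15% | 15% |
| +1 v 0 | counts | 53% | 28% | 18% |
| | proportion | 39% | 19% | 13% |

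Scoring the three categories as −1, 0, +1 does not help: 0 to 8% for +4 v +2.

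**4. A second model.** Let gains be Poisson with no losses, so P(increase) = 1 − exp(−mean). For 4 v 2 this is 1 − e⁻⁴ = 98.2% against 1 − e⁻² = 86.5%. With 10 per arm, the two arms differ by at most one subject 64% of the time. The Welch interval on counts excludes zero in 68% of trials; Fisher's exact test on the direction call reaches 0.05 in 0.5%.

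**5. Regional calls.** Section 8.12 reads images of each region but gives neither the number of regions nor a rule for combining them. Assume 2 to 8 regions, Poisson gains spread evenly, FT means of 2 to 4 and FT-SW at half. A tally of regions with an increase then excludes zero in about 30 to 61% of trials, against 39 to 68% with counts.

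**6. Counting error.** Take +4 v +2 with SD 1.5, and add reading error of SD e to each of the pre and post counts, so the SD of the change is √(1.5² + 2e²). For e = 1, 1.5 and 2 the count result falls from 79% to 53%, 36% and 26%. The proportion derived from the same noisy counts gives 12 to 13%.

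**The case against.** **Regional calls may keep much of the size.** If a call is made in each region, a subject who improves in five regions differs from one who improves in one. Step 5 shows that a tally could recover a good part of the information when gains are spread evenly. This stands, and it rules out an inference that a reader might draw: that the size is wholly lost once the call is made and no change to the analysis could help. What remains is that no tally is planned, size within a region is still lost, and gains concentrated in one region would weaken the tally. Stored images might also be re-read, though Section 8.12 does not promise an archive, and the CRF, which is not among the documents, might hold more than the protocol asks for.

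**The magnitudes are assumed.** This stands. Saturation needs FT gains of roughly 3 to 4 vessels per subject; at +1 v 0 the loss is modest, and counting error narrows the advantage further without removing it in the cases tried.

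**The yardstick is not the plan's.** Section 16.0 plans estimation without tests, and how often an interval excludes zero does not measure the ability to show equivalence. This stands as a limit on the percentages. It does not answer the main point: a direction call prevents estimation of the size of the gain.

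**Other measures could reveal a weaker device.** This also stands. Vessel number is one half of an and/or outcome. Backflow area and propulsion rate are recorded as numbers, although Table 1 summarises them only as proportions. Perometry, local tissue water and skin thickness have mean changes planned.

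**Conclusion.** The point holds for the vessel component of one NIRF outcome. That Section 8.12 asks for a direction while Table 1 names a number is a matter of text and depends on no assumption. Nor does the saturation case, in which a halved gain reads 10/10 in both arms.

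The size of the information loss does rest on assumptions: whole-number normal gains, one call per subject, 10 per arm and no counting error. On those terms, a halved effect at +4 or +3 is visible in about 35 to 98% of trials with counts and 0 to 15% with the proportion. At +1 v 0 the figures are 18 to 53% and 13 to 39%. They illustrate the loss and are not operating characteristics of this trial.

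A reader might infer that a weaker FT-SW would pass through the whole study unnoticed. The documents do not support that: the vessel summary can look the same in both arms, not will, and every other efficacy measure is captured numerically. This is a worthwhile, inexpensive improvement and not a flaw that undermines the study.

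**What to change.** - **Section 8.12:** replace the direction call with an instruction to count the intact fluorescent vessels in each imaged region of each arm, before and after treatment, and to record both counts. Derive increase, decrease or no change from the counts.
- **Table 1:** add the mean change in number of functional vessels for the affected arm and for the contralateral arm, each reported as the FT-SW minus FT difference with a 95% confidence interval. Keep the existing proportion as a supporting summary.

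**Cost:** two numeric fields per region in place of one category, and an added summary row. The images and the reader are already in the plan, and nothing is added for the subject. Reading takes slightly longer, and there will be some counting error where vessels overlap; the present call already requires the reader to compare vessels before and after.
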